6.5 Efficacy Analyses

All efficacy analyses will be presented using the All Treated patients analysis set, unless otherwise specified, by dose level and total. Analyses may also be performed using the subgroups listed in Section 5.9. Covariates are not considered for adjustment in analyses.

Response assessments, including SPEP/immunofixation, UPEP/immunofixation, SFLC, bone marrow assessments and plasmacytoma evaluation by imaging, as well as overall disease assessment will be listed.

6.5.1 Efficacy Endpoints

6.5.1.1 Objective Response Rate (ORR)

Objective response (OR) rate (ORR) is defined as the proportion of patients with best response sCR, CR, VGPR or PR per investigator. Patients whose disease response cannot be evaluated per IMWG will be considered as non-responder for calculating the ORR in the All Treated Patients analysis set. Patients whose first OR occurs after new antitumor therapy other than study treatment will not be counted as a responder.

The ORR per investigator and its exact two-sided 95% confidence interval using the Clopper-Pearson method ([Collett 1991](#)) will be calculated. This endpoint may also be tabulated by the subgroups defined in Section [5.9](#).

6.5.1.2 Complete Response Rate

Complete response (CR) rate is defined as the proportion of patients with best response sCR or CR per investigator. Patients whose disease response cannot be evaluated per IMWG will be scored as Not Evaluable for calculating the CR rate in the All Treated Patients analysis set. Patients whose first CR occurs after new antitumor therapy other than study treatment will not be counted as a CR when calculating CR rate.

The CR rate and its exact two-sided 95% confidence interval using the Clopper-Pearson method ([Collett 1991](#)) will be calculated. This endpoint may also be tabulated by the subgroups defined in Section [5.9](#).

6.5.1.3 Duration of Response

Duration of response is defined as the time from first documentation of objective response (sCR, CR, VGPR, or PR) to the first documentation of disease progression (PD) or to death due to any cause, whichever comes first. Disease progression includes radiologic evidence of tumor progression and/or clinical progression per investigator. Duration of response for patients who don't have additional response assessments after documentation of objective response will be censored as 1 day.

Duration of response data will be censored as described below:

- Patients who do not have disease progression and are still on study at the time of an analysis will be censored at the date of the last disease assessment documenting absence of progressive disease.
- Patients who have started an antitumor treatment other than the study treatment prior to documentation of disease progression will be censored at the date of the last disease assessment prior to start of new therapy.
- Patients who are removed from the study prior to documentation of disease progression will be censored at the date of the last disease assessment documenting absence of progressive disease.

Duration of response will only be calculated for the subgroup of patients achieving a sCR, CR, VGPR or PR. Duration of response will be analyzed using Kaplan-Meier methodology and Kaplan-Meier plots will be provided. The median duration of response and its two-sided 95% CI using the complementary log-log transformation method (Collett 1994) will be calculated for each expansion cohort and total.

6.5.1.4 Progression Free Survival (PFS)

Progression-free survival (PFS) is defined as the time from the start of study treatment to the first documentation of disease progression (PD) based upon the disease assessment per IMWG 2014 criteria or clinical progression, or to death due to any cause, whichever comes first. Specifically,

$$\text{PFS} = \text{Date of first documented PD or death} - \text{Date of first study treatment} + 1.$$

Patients who don't have post-treatment response assessments or death will be censored on the treatment start date (i.e., PFS is censored as 1 day). The same censoring rules outlined in Section 6.5.1.3 for the DOR will be applied to PFS.

PFS will be analyzed using the Kaplan-Meier methods and Kaplan-Meier plots will be provided. The median PFS and its two-sided 95% confidence intervals (CI) will be calculated using the complementary log-log transformation method (Collett 1994).

The analysis of PFS may be performed for each of the subgroups specified in Section 5.9.

6.5.1.5 Overall Survival (OS)

Overall survival is defined as the time from the start of study treatment to date of death due to any cause. Specifically,

$$\text{OS} = \text{Date of death} - \text{Date of first study treatment} + 1.$$

In the absence of confirmation of death, OS will be censored at the last date the patient is known to be alive. If the last recorded date where a patient is known to be alive is the date of first dose of study treatment, survival time will be censored on the treatment start date (i.e., OS duration of 1 day).

Overall survival will be analyzed using Kaplan-Meier methodology and Kaplan-Meier plots will be provided. The median OS and its two-sided 95% confidence intervals (CI) will be calculated using the complementary log-log transformation method (Collett 1994).

ATA incidence will be summarized by dose level and total for all treated patients.

6.6 Safety Analyses

The All Treated Patients analysis set will be used to summarize all safety endpoints, by dose level and total.

Adverse events will be coded using Medical Dictionary for Regulatory Activities (MedDRA, Version 20.1 or higher).

Laboratory values and adverse events will be graded according to the National Cancer Institute Common Terminology Criteria for Adverse Events (NCI CTCAE version 4.03).

Concomitant medications will be coded using WHO Drug (version: June 2017 or more recent).

6.6.1 Adverse Events

Adverse events will be summarized by MedDRA preferred term in descending frequency of occurrence unless otherwise specified. For incidence reporting, if a patient reports more than one AE that was coded to the same system organ class or preferred term, the patient will be counted only once for that specific system organ class or preferred term.

A treatment-emergent AE is defined as a newly occurring or worsening AE after the first dose of SEA-BCMA. An overall summary of AEs will be provided by dose level and total. Summaries of AEs will also be provided by dose level and total for the following, by preferred term, if not specified otherwise:

- All treatment-emergent AEs
- AEs related to SEA-BCMA
- Serious Adverse Events (SAEs)
- SAEs related to SEA-BCMA
- AEs leading to dose elimination of SEA-BCMA
- AEs leading to dose delay of SEA-BCMA
- AEs leading to dose interruption of SEA-BCMA
- AEs leading to dose reduction of SEA-BCMA
- AEs leading to treatment discontinuation
- AEs leading to death
- Infusion related reactions by preferred term
- Adverse Events considered as DLT
- Treatment-emergent AEs by system organ class, preferred term and maximum severity
- Grade 3–5 treatment-emergent AEs
- Treatment-emergent AEs by system organ class and preferred term

All adverse events, adverse events leading to treatment discontinuation, and adverse events leading to death will be listed.

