4.4.1. Discontinuation of Study Treatment

A subject's study treatment may be discontinued for any of the following reasons:

- PD
- AE
- Pregnancy
- Investigator decision
- Subject decision, non-AE
- Study termination by sponsor
- Other, non-AE

In Parts A and B (monotherapy), subjects who discontinue SEA-BCMA will be considered discontinued from study treatment. Subjects who discontinue from study treatment will remain on study for follow-up until withdrawal of consent, death, or study closure, whichever occurs first.

In Part C, subjects who discontinue SEA-BCMA and dexamethasone will be considered discontinued from study treatment. Subjects receiving dexamethasone who discontinue corticosteroid therapy may continue to receive SEA-BCMA as monotherapy with medical monitor approval. Subjects who discontinue SEA-BCMA will be considered discontinued from study treatment.

In Part D, subjects who discontinue SEA-BCMA, dexamethasone, and pomalidomide will be considered discontinued from study treatment. Subjects receiving dexamethasone who discontinue corticosteroid therapy may continue to receive SEA-BCMA and pomalidomide with medical monitor approval. Subjects who discontinue pomalidomide may continue to receive SEA-BCMA and dexamethasone with medical monitor approval. Subjects who discontinue SEA-BCMA will be considered discontinued from study treatment.

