7.7.3.1. Relationship of the Adverse Event to Study Treatment

The relationship of each AE to each study treatment (SEA-BCMA, and/or dexamethasone, and/or pomalidomide) should be evaluated by the investigator using the following criteria:

Related:

There is evidence to suggest a causal relationship between the drug and the AE, such as:

- A single occurrence of an event that is uncommon and known to be strongly associated with drug exposure (eg, angioedema, hepatic injury, Stevens-Johnson Syndrome)
- One or more occurrences of an event that is not commonly associated with drug exposure, but is otherwise uncommon in the population exposed to the drug (eg, tendon rupture)

Unrelated:

Another cause of the AE is more plausible (eg, due to underlying disease or occurs commonly in the study population), or a temporal sequence cannot be established with the onset of the AE and administration of the study treatment, or a causal relationship is considered biologically implausible

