9.3.9.2. Adverse Events

An overview of AEs will provide a tabulation of the incidence of all AEs, treatment-emergent AEs, treatment-related AEs, Grade 3 and higher AEs, SAEs, treatment-related SAEs, deaths, AEs leading to study treatment discontinuation, treatment-related TEAEs leading to study treatment discontinuation, TEAEs and treatment-related TEAEs leading to dose reduction and interruption. AEs will be defined as treatment-emergent if they are newly occurring or worsen following study treatment.

AEs will be listed and summarized by Medical Dictionary for Regulatory Activities (MedDRA), preferred term, SOC, severity, and relationship to study drug. In the event of multiple occurrences of the same AE with the same preferred term in 1 subject, the AE will be counted once as the occurrence. The incidence of AEs will be tabulated by preferred term and treatment

group. AEs leading to premature discontinuation of study drug will be summarized and listed in the same manner.

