Appendix A Imputation of Partially Unknown Adverse Event Dates

For an adverse event (AE) with a partial start or end date, if it can be determined that the event occurred prior to the first dose of any study treatment, the partial date will not be imputed; otherwise, the AE partial date will be imputed using the rules described below.

- a **A. AE occurred prior to the first dose of any study treatment**, i.e., satisfies either i or ii below:
 - i. Onset date is prior to the first dose date
 - ii. (Onset date is completely missing or the same as the first dose date) and (Onset Period is "started before the signing of consent" or "started after consent but before the first dose of any study treatment")
- 5. **B. AE occurred after the first dose of any study treatment**, i.e., satisfies either i or ii below:
 - i. Onset date is after the first dose date
 - ii. (Onset date is completely missing or the same as the first dose date) and (Onset Period is "started after first dose of any study treatment" or missing)
- b Note: compare AE onset date with the first dose date on the common precision only for all the date comparisons described in A and B above; e.g., "2019" is considered greater than "2018-xx-xx"; "2019-03" is considered equal to "2019-03-xx". Issue a WARNING to the log when (onset date is completely missing or the same as the first dose date) and Onset Period is missing.

For AE occurred after the first dose of any study treatment (see B. above) only:

- Impute incomplete AE start date as the followings:
 - ❖ AE day only is missing: if the month/year is the same as the month/year of first dose of any study treatment, AE start date will be imputed as the first dose date of any study treatment; if the month/year is after the month/year of first dose of any study treatment, AE start date will be imputed as the first day of the month
 - ❖ AE day and month are missing, or month only is missing: if the year is the same as the year of first dose of any study treatment, AE start date will be imputed as the first dose date of any study treatment; if the year is after the year of first dose of any study treatment, AE start date will be imputed as January 1st
 - ❖ AE day, month and year are missing, or year only is missing: AE start date will be imputed as the first dose date of any study treatment
- Impute incomplete AE end date as the followings when AE outcome is "recovering/resolving", "recovered/resolved", "recovered/resolved with sequelae", or "fatal":

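### The SAP specifies relatedness, dose-action and exposure outputs for SEA-BCMA only, so toxicity tied only to dexamethasone or pomalidomide cannot be identified in those tables for Parts C and D

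*SAP*

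**What the plan says.** Combination safety is a primary objective, and relatedness of AEs is part of the primary endpoint (Table 1 in section 2 of both documents).

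**Protocol.** Section 7.7.3.1 sets causality per drug: "The relationship of each AE to each study treatment (SEA-BCMA, and/or dexamethasone, and/or pomalidomide) should be evaluated by the investigator". Section 9.3.9.2 plans an overview that includes treatment-related AEs and SAEs and "TEAEs and treatment-related TEAEs leading to dose reduction and interruption", with no restriction to one drug. It defines emergence generally: "AEs will be defined as treatment-emergent if they are newly occurring or worsen following study treatment". Section 4.4.1 lets a partner drug stop alone; for Part D, "Subjects who discontinue pomalidomide may continue to receive SEA-BCMA and dexamethasone with medical monitor approval". It has a parallel rule for dexamethasone in Parts C and D.

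**SAP.** Section 6.6.1 lists AEs related to SEA-BCMA, "SAEs related to SEA-BCMA", and four dose-action tables (elimination, delay, interruption, reduction), each naming SEA-BCMA, such as "AEs leading to dose reduction of SEA-BCMA". Emergence is tied to the same drug: "A treatment-emergent AE is defined as a newly occurring or worsening AE after the first dose of SEA-BCMA". Appendix A uses a different anchor: "AE occurred prior to the first dose of any study treatment". Section 6.4 gives exposure and intended dose intensity for the two SEA-BCMA schedules. Sections 8.1 and 8.2, which record changes from plan, do not mention the narrowing.

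**The concern.** In a combination cohort, tolerability includes whether subjects can stay on the whole regimen. If a partner drug is cut or stopped for toxicity while SEA-BCMA continues unchanged, that bears directly on the primary objective for Parts C and D. The protocol collects causality by drug and plans tables that would show such events. The SAP, which governs what is produced, names only one of the three drugs in every table of this kind. A reader of the study report could then see how often an event occurred, but not that it was attributed to a partner drug or led to a change in that drug.

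**Working it through.** **1. Which drug does each SAP output name?**

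| Output | Drug named in SAP | Protocol 9.3.9.2 |
|---|---|---|
| Related AEs | SEA-BCMA | Treatment-related |
| Related SAEs | SEA-BCMA | Treatment-related |
| AEs leading to elimination, delay, interruption, reduction (4 tables) | SEA-BCMA | Reduction and interruption, no drug named |
| AEs leading to stopping treatment | None | Study treatment |
| Count of patients with a dose modification (6.4) | None | Not applicable |
| Duration for exposure, intended dose intensity (6.4) | SEA-BCMA schedules | Not applicable |

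Six of six drug-specific AE tables (2 relatedness + 4 dose-action) name SEA-BCMA; none names dexamethasone or pomalidomide.

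**2. Do the exposure formulas fit the partner drugs?** SAP 6.4 covers dosing every 2 weeks (last dose date + 14) and weekly dosing for two cycles followed by every 2 weeks (+7 or +14). Dexamethasone is weekly in every cycle (Protocol 5.3.3). Pomalidomide is daily on Days 1 to 21 of 28 (Protocol 5.4.3). Neither formula fits either drug.

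**3. Can an event change a partner drug and leave SEA-BCMA alone?** Yes, under the protocol's own tables. Grade 2 insomnia leads to a dexamethasone reduction (Table 6), and a Grade 1 AST or ALT elevation leads to withholding pomalidomide (Table 7). For Grade 1 and 2 toxicity, Table 5 continues SEA-BCMA unchanged. Such events enter none of the four dose-action tables and, because of their grade, not the Grade 3–5 table.

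**4. What happens to an isolated stop?** Under Protocol 4.4.1, study treatment is discontinued when SEA-BCMA stops or when all drugs stop. Stopping only dexamethasone or only pomalidomide meets neither condition. Read this way, the SAP's discontinuation table would probably omit the event. The SAP does not say so itself.

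**5. How many subjects?** The Part sizes reproduce the planned total: 45 + 20 + 60 + 6 = 131. Parts C and D give 60 + 6 = 66, and 66/131 = 50.4%. All 66 are to receive dexamethasone and 6 of them also pomalidomide. These are planned maxima.

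The documents give no rate for partner-drug-only events. As an assumption, take 10% to 50% of subjects with at least one:
- Expected number in Parts C and D: 66 × 0.10 = 6.6 to 66 × 0.50 = 33.
- Chance of at least one in Part D (n = 6): 1 − 0.90^6 = 47% to 1 − 0.50^6 = 98%.

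**6. How large is the treatment-emergence gap?** On Cycle 1 Day 1 the partner drugs precede SEA-BCMA by 1 to 3 hours (Protocol 5.3.3 and 5.4.3). An AE starting in that window is not emergent under SAP 6.6.1 unless it later worsens, but falls after first dose under Appendix A. The window is longer only if SEA-BCMA is delayed.

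**The case against.** The best reply is that little is lost. SAP 6.6.1 tabulates all treatment-emergent AEs, Grade 3–5 events, SAEs and fatal AEs whatever their cause, and lists every AE. This stands. A reader might infer that partner-drug toxicity goes untabulated, or that the combinations will look better tolerated than they were. The documents support neither, because type, incidence, severity and seriousness are all still reported. Only attribution and action taken by drug are missing.

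Second, the discontinuation table and the modification count in SAP 6.4 name no drug, and could include partner drugs. This stands too. The 6.4 count, however, is not linked to AEs or preferred terms, so it cannot show which toxicity caused a change.

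Third, Table 5 has no relatedness qualifier and acts on SEA-BCMA for Grade 3–4 haematologic and Grade 3 or higher nonhaematologic toxicity. Many severe events that interrupt pomalidomide could therefore also reach a SEA-BCMA table. A reader might construct a Part D case in which one subject stops pomalidomide for toxicity and the tables show none of six. The documents do not establish that result. The clear gap is lower-grade toxicity that touches only a partner drug, plus attribution at any grade.

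Fourth, this is a SEA-BCMA trial, and Protocol 9.3 lets the SAP depart from protocol analysis methods without an amendment if site conduct is unaffected. That permits the narrowing. It does not answer a primary objective about combinations, and the SAP does not list the change.

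**Conclusion.** The point holds as a gap in by-drug reporting. For up to 66 of 131 planned subjects, the SAP specifies no relatedness, dose-action or exposure output for dexamethasone or pomalidomide, although causality is collected per drug and the protocol's tables are not limited to SEA-BCMA. The events remain in the overall tables and listings. The number of subjects with such an event is unknown, and the 10% to 50% range is only an illustration.

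The statement about isolated discontinuation rests on reading the SAP's table with Protocol 4.4.1 and is probable, not certain. The treatment-emergence mismatch is real but small, and is a matter of consistency. No sample size or error rate is affected, since no hypothesis is tested. The change is worth making because it is cheap and serves a primary objective.

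**What to change.** In SAP 6.6.1, for Parts C and D:
- Add AEs and SAEs related to each study drug and to any study drug.
- Add AEs leading to modification or discontinuation of each drug and of any drug.
- State that the discontinuation table includes isolated stops of a partner drug.
- Date treatment-emergence from the first dose of any study treatment, in line with Appendix A.

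In SAP 6.4, add dexamethasone exposure, and pomalidomide exposure where dosing data allow. Record the change as SAP section 1 requires: an amendment before database lock, or documentation in the study report.

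The cost is a few more tables. Relatedness needs no new data, because causality per drug is already collected. Two checks come first. The AE items in Protocol 7.7.3.2 do not include action taken, so confirm that the CRF holds it for each drug. Pomalidomide is self-administered after Cycle 1 Day 1 (Protocol 6.5.3.1), while Protocol 5.8 describes only site-administered doses, so confirm that those doses are recorded. If either is missing, limit the affected table to what the data support and say so. Tables built from existing data need no protocol amendment under Protocol 9.3.
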